**A Double-Blind Randomized Controlled Trial on the Efficacy of Hydrocolloid
Dressing vs. Topical Antibiotic on Wound Healing of Post-Punch Biopsy
Wounds Among Patients in a Tertiary Hospital in Manila**

[name] [name]

[name], FPDS

University of Santo Tomas Hospital, [name]

Department of Dermatology

TITLE: A Double-Blind Randomized Controlled Trial on the Efficacy of Hydrocolloid Dressing vs. Topical Antibiotic on Wound Healing of Post-Punch Biopsy Wounds Among Patients in a Tertiary Hospital in Manila

[name], [name]

Resident, Department of Dermatology; Consultant, Department of Dermatology

PROJECT SUMMARY

Rationale:

Objectives: The main objective of this study is to determine the efficacy of using hydrocolloid dressing on wound healing of post-punch biopsy wounds vs topical antibiotic. Specifically, it aims to measure the following parameters: the presence or absence of infection, the clinical estimate of reepithelialization, the clinical estimate of wound closure, scar formation, pigmentation of scar, and the cosmetic appearance of the wound.

Methodology and Population: The study is a double-blind randomized controlled trial which will be conducted at the Dermatology outpatient department and the private clinics of dermatology consultants of the University of Santo Tomas Hospital. Patients who will be included are those who are 18 to 64 years of age with clean cutaneous lesions. Excluded from this study are those who have infected wounds, those who have conditions with poor tendency to heal including diabetes mellitus, peripheral vascular disease, history of keloid formation, those currently receiving anticoagulation therapy or systemic corticosteroids, and those known to have hypersensitivity to topical antibiotics.

Time Frame: 6 months

Expected Outcomes: The primary outcome measure is the proportion of patients who achieved better overall healing when treated with hydrocolloid dressing.

GENERAL INFORMATION**PROTOCOL TITLE:**

**A DOUBLE-BLIND RANDOMIZED CONTROLLED TRIAL ON THE
EFFICACY OF HYDROCOLLOID DRESSING VS. TOPICAL ANTIBIOTIC ON
WOUND HEALING OF POST-PUNCH BIOPSY WOUNDS AMONG
PATIENTS IN A TERTIARY HOSPITAL IN MANILA**

NAME AND ADDRESS OF SPONSOR/FUNDER:

NOT APPLICABLE

NAME AND ADDRESS OF AUTHORS:

[name] [name]

[name], FPDS

University of Santo Tomas Hospital, [name]

BACKGROUND

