Skin biopsies play an essential role in the verification or confirmation of the diagnosis of patients with dermatologic disorders. The punch biopsy, one of the frequently performed types of skin biopsies, is an incisional method that makes use of a cylindrical blade to obtain a specimen with a fuller thickness of the skin as compared to a shave biopsy. It is a procedure that has a low-risk of developing surgical site infections due to the short operative time and shallow wound depth. The most commonly used skin punch sizes range from 2 mm to 6 mm in diameter. Punch biopsies of less than 4 mm in size do not need to be closed with sutures. Obtaining an adequate tissue sample for histopathologic evaluation while preventing patient disfigurement is important.^[1]

Wound healing is a complex biological process where the main goal of clinical intervention is the promotion of tissue restoration.^[2] Acute wounds are wounds that follow a predictable and timely repair process which results in the restoration of sufficient anatomical and functional integrity if healing proceeds normally.^[3] In the pathophysiology of acute wound healing, there are four overlapping phases of the normal wound healing process namely coagulation, inflammation, granulation tissue formation, and remodeling phase. Neutrophils, macrophages, and platelets provide growth factors and provisional matrices that are required for the recruitment of epidermal and dermal cells into the wound bed during the coagulation and inflammatory phases of healing. The proliferative phase begins 3 days after injury and is characterized by increased keratinocyte and fibroblast proliferation, migration, and extracellular membrane synthesis. During this stage, angiogenesis or neovascularization also occurs. The tissue has a granular appearance due to the presence of blood vessels (granulation tissue). Finally, 1 to 2 weeks after injury,

differentiated fibroblastic cells (myofibroblasts) present in the granulation tissue begin to remodel the extracellular matrix. Acellular scar formation is caused by extracellular matrix remodeling followed by apoptosis of resident cells.^[4]

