Hydrocolloid is a type of dressing in which a "hydrophilic gelable mass is applied in a semisolid form to a flexible semipermeable carrier." Hydrocolloids were originally made as small square pieces in 1985. In 1989, a "thin" version was developed wherein these dressings have little or no fluid retention ability and are less permeable than the standard films and are used as post-operative dressings or as secondary retention products over primary dressings. Hydrocolloid dressings are most commonly utilized with the treatment of chronic wounds such as leg ulcers and pressure ulcers, however they can also be used with good effect for the treatment of a variety of acute wounds where their ability to facilitate debridement, absorb excess fluid and provide a barrier to infection is equally valuable.^[5]

Locally, in the Philippines, due to high rates of infection, topical antibiotics are routinely applied as wound care and prophylaxis despite obtaining clean wounds. In this study, we will investigate whether hydrocolloid dressings can be used as a treatment modality for the healing and care of post-punch biopsy sites.

REVIEW OF RELATED LITERATURE

Surgical Wounds

In the management of surgical wounds, hydrocolloid dressings have been used as primary and secondary dressings for sutured wounds and wounds with secondary intention healing.^[5]

The use of hydrocolloids following excision of pilonidal sinuses have been reported by Viciano *et al.* through a prospective randomized trial involving 38 patients in which the researchers compared a hydrocolloid (Comfeel with Varihesive/Duoderm) and conventional gauze. Median healing time in the control group was 68 days in comparison to the experimental group which was 65 days. One-third of the cultures in the control group developed pathogens compared with 1 out of 23 patients with the hydrocolloid group, however these results were deemed statistically insignificant. Pain was assessed as significantly less in the hydrocolloid group in the first four weeks post-operation compared with those in the control group in which the conclusion was made that the use of hydrocolloid dressings leads to a reduction in pain but no effect on healing times.^[6]

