A study by Estienne and Di Bella compared Granuflex/Duoderm with traditional dressings which made use of hypochlorite irrigation and packing with paraffin gauze in 40 patients for pilonidal fistula. The hydrocolloid dressing was first applied on the third postoperative day after an iodoform gauze pack was removed which was applied in theater. Dressings were changed on alternate days, but was extended to 3-5 days later on and results showed that wounds with hydrocolloid dressings had complete healing in an average of 6 weeks compared with 10 weeks with the traditional dressings.^[7]

Michie and Hugill compared Granuflex/Duoderm Extra Thin hydrocolloid dressing with an impregnated gauze (Xeroform) in 28 patients with 40 wounds after an elective surgery to assess the effects of the dressings on incisional healing. One-half of every incision was covered with each of the dressings under investigation as each patient served as their own control. Wounds were assessed after a period of 2 to 3 days, 7 to 10 days, 4 weeks, and 7 months postoperatively. No incision showed any evidence of infection and during suture removal, hydrocolloid dressings were assessed to contain exudate, protect the wound, and facilitate mobility and personal hygiene more effectively compared with the impregnated gauze dressing. When assessment was done after 4 weeks, scar segments covered with hydrocolloid dressings showed better appearance in terms of color, evenness, and suppleness compared with the Xeroform gauze, however these differences were no longer observed 7 months after the elective surgery.^[8]

A study by Hulten showed that soiling which commonly occurs with wounds dressed with traditional gauze were not observed in 89% of 340 patients who had undergone colorectal surgery with stoma creation and dressed with hydrocolloid. The study also showed that 92% of the patients studied had no wound infections encountered.^[9]

Burns

A report on the use of hydrocolloid dressing in the treatment of burns by Hermans and Hermans in 1984 showed that the use of Granuflex/Duoderm in 24 patients had favorable healing rates compared with those treated with silver sulfadiazine cream in both superficial and deep partial thickness burns.^[10]

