In a study by Wright *et al*, 67 patients with partial thickness burns managed as outpatients were treated with hydrocolloid dressings (Granuflex/Duoderm) versus conventional dressing (Bactigras) to compare the two products. The healing time (median 12 days) were comparable for both products in this study, however the quality of healing was rated “excellent” in 56% of the participants treated with Granuflex/Duoderm versus 11% in the group treated with Bactigras. The authors in this study suggested to use Granuflex/Duoderm as “first-choice dressing in the management of partial skin thickness burns”.^[11]

Traumatic Wounds

A study done by Heffernan and Martin compared Granuflex/Duoderm Extra Thin with a perforated film absorbent dressing in managing 96 patients with lacerations, abrasions and minor operation incisions. The study showed similar results for healing time for both interventions; however, those patients using hydrocolloid dressings experienced less pain, required less analgesia, and were able to carry out activities of daily living without their wounds getting affected.^[12]

Pediatric Wounds

A study done by Schmitt *et al*. compared hydrocolloid dressing with adhesive skin tapes on post-operative wounds in 170 children. Effective skin closure was comparable in both interventions but hydrocolloids were observed to be more secure, remaining in place in 69 children compared with adhesive skin tapes.^[13]

SIGNIFICANCE OF THE STUDY

This study can provide a potential option to promote faster healing of post-operative wounds particularly for skin punch biopsy used in the field of Dermatology.

It will encourage Filipino dermatologists to reduce the routine use of prophylactic topical antibiotics as post-biopsy care heralding better antibiotic stewardship practices.

MAIN OBJECTIVE

The main objective of this study is to determine the efficacy of using hydrocolloid dressing on wound healing of non-sutured post-punch biopsy sites in comparison to gauze dressing impregnated with topical antibiotics (mupirocin ointment) at the Dermatology outpatient department and the private clinics of dermatology consultants of the University of Santo Tomas Hospital.

SPECIFIC OBJECTIVES

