Specifically, this study aims to compare the efficacy of hydrocolloid dressing after 5 days post-punch biopsy by measuring the following parameters: absence or presence of infection, clinical estimate of reepithelialization, clinical estimate of wound closure, scar formation, pigmentation of scar and cosmetic appearance of wound.

METHODOLOGY

A. Study Design

This is a double blind randomized controlled trial that will be conducted at the outpatient department of the University of Santo Tomas Hospital Department of Dermatology. Permission letters from the Head of Ambulatory Care Services (ACS), the Data Privacy Officer (DPO), and the Medical Director of UST Hospital will be obtained prior to the implementation of this study. Permission letters from the USTH Dermatology consultants for their private patients will be obtained prior to the implementation of this study.

[figure not shown]

Figure 1. Schematic diagram of the study design

B. Patient Selection, Recruitment and Withdrawal

Adult patients 18 to 64 years old with clean cutaneous lesions who will undergo skin punch biopsy using a 3-mm disposable biopsy puncher shall be included in the study.

Patients will be recruited from the UST Hospital outpatient department and from the private clinics of the UST Hospital Dermatology consultants. Patients who have infected wounds, patients who have conditions with poor tendency to heal including diabetes mellitus, peripheral vascular disease, history of keloid formation, patients currently receiving anticoagulation therapy or systemic corticosteroids, and patients known to have hypersensitivity to topical antibiotics shall be excluded from the study.

Participants may request to withdraw from the study at any time. A participant may also be withdrawn from the study if the primary investigator believes that the participant was non-compliant with the treatment guidelines or develops severe and intolerable adverse effects (e.g. hypersensitivity reaction) secondary to the treatment given.

C. Randomization and Blinding

Randomization

Assignment of participants to the experimental (hydrocolloid dressing) or control group (topical antibiotic) will be done using the fishbowl method by a research assistant.

Blinding

Participants and the physician assessors will be blinded with the treatment assigned.

D. Baseline Data Collection

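### At day 5, scar formation, pigmentation and cosmetic appearance each hold an 'unhealed' level beside the quality levels, so one all-level p-value cannot be read as a scar difference

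*Combined protocol and SAP*

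**What the plan says.** There is one protocol with a short statistical section. The Specific Objectives say "this study aims to compare the efficacy of hydrocolloid dressing after 5 days post-punch biopsy by measuring the following parameters" and list infection, reepithelialization, wound closure, scar formation, scar pigmentation and cosmetic appearance. The sections on data collection and assessment also give day 5, and the text describes no later outcome visit (the schematic, Figure 1, could not be read).

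In the Scoring Criteria, scar formation (item 4) has four levels, the first being 'unhealed'. Pigmentation (item 5) has four levels and cosmetic appearance (item 6) has five; in both, the first is 'indeterminate or unhealed'. Reepithelialization and wound closure are rated separately, in bands.

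The statistical section assigns Fisher's exact or chi-square tests to frequencies, two-sided at 0.05. Dummy Table 2 lists the unhealed levels as ordinary rows and has a single p-value column. Nothing says that the unhealed level is excluded, analysed separately or ordered relative to the others.

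The Project Summary says "The primary outcome measure is the proportion of patients who achieved better overall healing when treated with hydrocolloid dressing", without stating which items enter that judgement. The sample size of 28 per group is computed for a mean scar appearance score.

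**The concern.** The protocol's own background makes unhealed wounds at day 5 plausible. It dates the start of remodeling with "Finally, 1 to 2 weeks after injury" and adds that "Acellular scar formation is caused by extracellular matrix remodeling followed by apoptosis of resident cells". If an appreciable share of wounds is unhealed, each of the three items answers two questions at once: whether the wound has healed, and what it looks like if it has. A single p-value over all levels cannot say which answer differs between arms.

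If one dressing simply closes more wounds by day 5, a row headed scar formation, pigmentation or cosmetic appearance can be significant although scar quality is the same in both arms. It could then be reported as a scar or cosmetic benefit. Because the primary outcome does not define better overall healing, the same misreading could enter there.

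**Working it through.** **1. The plan's own figure.** Inputs from the sample-size section: means 8.38 and 7.23, SD 1.5, two-sided alpha 0.05, power 80%.
- d = (8.38 − 7.23)/1.5 = 1.15/1.5 = 0.767.
- Normal approximation: n = 2(1.96 + 0.84)²/0.767² = 26.7, so 27 per arm.
- Exact t-test: 27.70, so 28 per arm, with power 0.804.

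The stated 28 per group reproduces. It applies to a t-test on a mean score, and none of the six outcomes in the Scoring Criteria is such a score.

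**2. One worked table.** The counts are assumed. Scar formation, 28 per arm, in the order unhealed / atrophied / fine-line / hypertrophied: hydrocolloid 6/4/16/2, antibiotic 17/2/8/1. Among healed wounds (22 v 11) the proportions are identical. Column totals are 23, 6, 24 and 3, so the expected counts per arm are 11.5, 3, 12 and 1.5.
- Chi-square = 2 × (5.5²/11.5 + 1²/3 + 4²/12 + 0.5²/1.5) = 2 × (2.630 + 0.333 + 1.333 + 0.167) = 8.93 on 3 df, p = 0.030. Fisher's exact test gives p = 0.019.
- Unhealed v all other levels: Fisher p = 0.006.
- Scar type among healed wounds: p = 1.00.

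The all-level result comes entirely from the unhealed row.

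**3. How often this happens.** Simulation of 20,000 trials per scenario, 28 per arm, Fisher's exact test at 0.05, one rating per wound, identical quality among healed wounds in both arms. Assumed mixes among healed wounds, in the order of the scales: scar formation 20/70/10%; cosmetic appearance 10/20/40/30%; pigmentation 40/50/10%. All healing rates are assumptions.

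| Healed, arm A v arm B | Scar formation | Cosmetic appearance | Pigmentation |
|---|---|---|---|
| 60% v 20% | 79% | 75% | 78% |
| 50% v 20% | 55% | 48% | 53% |
| 40% v 20% | 28% | 24% | 26% |
| 30% v 20% | 10% | 9% | 9% |
| 50% v 50% | 5% | 5% | not run |

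For scar formation, the other 10-point gaps tried (50 v 40, 20 v 10, 15 v 5, 90 v 80) gave 9–12%; 10% v 5% gave 2% and 20% v 20% gave 4%. If 30% of healed wounds in both arms are called indeterminate, the first four pigmentation figures fall to 52%, 32%, 17% and 6%. Pearson's chi-square gives mostly lower figures (scar formation: 75%, 49%, 23% and 7% in the first four rows). A Fisher test among healed wounds only rejects in no more than 5% of trials in any of these scenarios, so the excess comes from the unhealed level.

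**4. Is low power part of the same fault?** Assume a real difference among healed wounds (20/70/10% v 40/40/20%) and equal unhealed shares. Fisher power, all-level v healed-only: 23% v 26% at 50% unhealed, 15% v 16% at 70%, 10% v 9% at 80%, 2% v 2% at 90%. With no unhealed wounds it is 49%. The two tests lose power almost together, so the loss comes essentially from having few scorable wounds.

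**The case against.** **The test is valid.** A reader might infer that the planned test has an inflated error rate. It does not. It correctly tests for any difference in distribution, and it rejects in 5% or fewer of trials when the distributions are equal. Wound healing is the main objective, so an unhealed wound is an on-topic outcome, and keeping every assessed wound in the table avoids a subset formed after randomization. All of this stands. What remains is what the p-value may be said to show.

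**Healing may not differ.** A reader might infer that faster healing with hydrocolloid is expected and the artefact therefore likely. The documents do not settle this. The protocol hopes that "This study can provide a potential option to promote faster healing of post-operative wounds", and its review includes a pilonidal study with healing in 6 v 10 weeks and a burns report of favourable healing rates. But another pilonidal trial concluded that "the use of hydrocolloid dressings leads to a reduction in pain but no effect on healing times", a second burns trial reports "The healing time (median 12 days) were comparable for both products in this study", and a trial in minor wounds found similar healing times. With similar healing the distortion is small, and the 40-point gap behind the largest figure has no source in the documents.

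**Day 5 may be scorable.** A reader might infer that no scar can be rated at day 5. The Assessment section says the healing phases overlap, so some wounds may be. The review does say "When assessment was done after 4 weeks, scar segments covered with hydrocolloid dressings showed better appearance in terms of color, evenness, and suppleness", but in the same sentence it reports that this advantage was gone at 7 months. It neither proves nor rules out a day-5 difference.

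**Low power.** A reader might blame low power on the mixed scale. Step 4 shows that it is a limit of timing and sample size.

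**The shell is blank, and Table 2 already prints the unhealed rows.** Both are true. One test per item is the natural reading, not an explicit statement, and a careful reader could see where a difference arises. The p-value still does not separate the two. Three assessors also rate each wound with no stated rule for combining ratings, so the simulated single rating is a simplification.

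**Conclusion.** The point holds as a matter of interpretation and reporting. For three of the six day-5 outcomes, the natural reading of the plan gives one p-value that mixes healing status with scar quality, so it cannot support a statement about scars. The size depends on the difference in day-5 healing between arms, which the documents do not give. With identical scar quality and the assumed mix, the scar-formation test is significant in about 80% of trials at 60% v 20% healed, 55% at 50% v 20%, 28% at 40% v 20%, 9–12% at 10-point gaps, and 5% or less at equal shares.

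The documents do not show that healing will differ, and they do not say that these items enter better overall healing; they leave that open. Overlap with the separate wound-closure bands was not examined. Separately, and without any assumption about healing, the stated 80% power does not apply to any of the six categorical outcomes. The plan should be amended on both counts.

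**What to change.** 1. In the statistical section and Table 2, replace the all-level p-value for the three items with one comparison of the unhealed (or 'indeterminate or unhealed') level against all other levels, with all assessed wounds as denominator. Label it healing status for scar formation, and healing or scorability for the other two. Record 'indeterminate' and 'unhealed' as separate levels on the evaluation sheet.
2. Show the quality levels among scorable wounds by arm, with denominators, as description without a p-value, because that subset forms after randomization.
3. State that a difference in the unhealed level at day 5 is not evidence of better scar quality, including within better overall healing in the primary outcome.
4. Restate the sample size: 28 per group gives 80% power only for a 1.15-point difference in a mean scar appearance score with SD 1.5, and this power does not apply to the day-5 categorical outcomes.

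**Cost.** Changes to wording, to Table 2 and to the evaluation sheet; no extra visit or patients. The trial gives up any test of scar quality. Descriptive denominators may be small: at 20% healed, 28 × 0.20 = 5.6, or about 6 scorable wounds in an arm. The power statement becomes less favourable: the unhealed comparison has Fisher power 0.82 at 60% v 20% healed but 0.08 at 30% v 20%, again under assumed rates.

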On the first visit, informed consent will be obtained from the patient. Afterwards, the following data will be recorded by the primary investigator on the baseline general information sheet: study code assigned to each individual patient, age, sex, and anatomic sites involved.

Photographs will be limited to the skin punch biopsy sites and will be taken at baseline using a DSLR camera with uniform distance (3 inches) and lighting.

On the 5th day after the skin punch biopsy procedure, the following data will be recorded by the physician assessors: the presence or absence of infection, the clinical estimate of reepithelialization, the clinical estimate of wound closure, scar formation, pigmentation of scar, and the cosmetic appearance of the wound. The primary investigator will then collect the wound evaluation sheets from the physician assessors. Photographs of the biopsy site will also be taken.

E. Intervention

Before the biopsies will be performed, the sites will be cleansed with 70% isopropyl alcohol and anesthetized intradermally with 1% lidocaine hydrochloride.

No suture, electrocautery, aluminum chloride or other hemostatic agents will be applied to the biopsy sites to avoid inhibition of wound healing inherent with these agents.

Once bleeding will be controlled by pressure, wounds will be dressed with either a 1-inch size Duoderm Control Gel Formula hydrocolloid dressing or gauze dressing impregnated with mupirocin ointment covered by a transparent dressing (Tegaderm). Dressings will be left in place for 5 days, after which the dressings will be removed and will be cleansed with water to remove any exudate.

F. Assessment

For this study, wound assessment will be done after 5 days. Dermoscopy and photographs of the wounds will be taken for every evaluation.

According to a study entitled “Pathophysiology of Acute Wound Healing” by [name] et. al. published in Elsevier Clinics in Dermatology in 2007, there are three phases of wound repair that overlap in time. These are the inflammatory reaction phase, proliferation phase, and remodeling phase. Days after initial injury, the wound would be in the proliferative phase where there would be reepithelialization of the wound, the establishment of appropriate blood supply, and reinforcement of the injured dermal tissue.^[14]

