The possible side effect of hydrocolloid dressing is irritation of the skin. Treatment on patients who will experience any adverse side effects will be immediately stopped.

To minimize the risk of COVID-19 exposure, all safety measures in accordance with the IATF guidelines will be observed.

BENEFITS

The benefit that the patient will acquire from this study is better clinical outcomes of the post-biopsy site. This study can also help reduce medical costs and patients are suggested with alternative options which can be potentially used as one of the treatment modalities for post-biopsy sites.

INCENTIVES AND COMPENSATION

All of the dermatologic consultations and medications of the participants for the duration of the study will be free of charge. Transportation allowance of PHP 100.00 will be provided to the participant on their visit on the 5th day. Management, consultation, and treatment of adverse effects resulting from the participation in this study will be free of charge. No other form of monetary compensation will be provided to the patients for their participation. Patients will be informed of the results of the study once it has been completed.

SCORING CRITERIA FOR EVALUATION OF WOUND

Objective assessment is based on a study by Armstrong et. al. in 1986 entitled "Punch biopsy wounds treated with Monsel's solution or a collagen matrix".^[16] For this study, the assessment will be done as follows:

(1) infection (absent, millimeters of surrounding erythema or equivocal findings; or present, as inferred by indurated erythema or purulent discharge);

- (2) clinical estimate of reepithelialization (rated on a scale of (a) 0% to 25%, (b) 26% to 50%, (c) 51% to 75%, and (d) 76% to 100%);
- (3) clinical estimate of wound closure (rated on a scale of (a) 0% to 25%, (b) 26% to 50%, (c) 51% to 75%, and (d) 76% to 100%)
- (4) scar formation (unhealed; depressed or atrophied; normal fine-line scar; or hypertrophied scar or keloid);
- (5) pigmentation of scar (indeterminate or unhealed; normal; hyperpigmented; or hypopigmented);
- (6) cosmetic appearance of wound (acceptance of patient: indeterminate or unhealed; poor; fair; good; excellent)

DUMMY TABLES

Table 1. Baseline demographic and clinical characteristics

	Total	Hydrocolloid	Topical	P-value
		Dressing	Antibiotic	
Frequency (%); Mean \pm SD				
Age, years				
Sex				
Male				
Female				
Indications for Skin				
Punch Biopsy				
...				

Table 2. Scoring Criteria for Evaluation of Wound

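### The hypersensitivity exclusion names only topical antibiotics, so a patient with a known reaction to either study dressing is eligible and can be randomized to wear it

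*Combined protocol and SAP*

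**What the plan says.** The exclusion criteria appear twice. Methodology, section B (Patient Selection, Recruitment and Withdrawal) states that "patients known to have hypersensitivity to topical antibiotics shall be excluded from the study". The Project Summary, under Methodology and Population, excludes "those known to have hypersensitivity to topical antibiotics". No other product is named in either place.

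Section E (Intervention) says that "wounds will be dressed with either a 1-inch size Duoderm Control Gel Formula hydrocolloid dressing or gauze dressing impregnated with mupirocin ointment". In the control arm a transparent film dressing (Tegaderm) goes over the gauze. In both arms, "Dressings will be left in place for 5 days".

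On harm, the Risks section says: "The possible side effect of hydrocolloid dressing is irritation of the skin". It then has treatment stopped at once for an adverse effect of any degree. Section B lets the investigator withdraw a participant who "develops severe and intolerable adverse effects (e.g. hypersensitivity reaction) secondary to the treatment given". The Safety Evaluation section has pruritus, burning and stinging asked about, and other signs checked, at the follow-up visit in both arms.

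**The concern.** The protocol accepts that a known reactor to a study product should not enter the trial, but applies this to only one of the products that participants wear. Someone who reports at screening a past reaction to hydrocolloid, or to a film dressing, passes every written criterion. If that person draws the arm in question, the product stays on a fresh wound for 5 days.

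What is at stake is first a foreseeable and avoidable reaction in a participant. Second, with 28 patients per arm, one or two such reactions would be visible in any listing of adverse effects, and a reader could not tell whether they reflect the product in ordinary use or the enrolment of people already known not to tolerate it.

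**Working it through.** **1. Products set against the exclusion**

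| Product (Methodology E) | Arm | Known hypersensitivity excluded? |
|---|---|---|
| Mupirocin ointment in gauze | Control | Yes, as a topical antibiotic |
| Transparent film (Tegaderm) | Control | No |
| Duoderm hydrocolloid | Hydrocolloid | No |

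No other section closes the gap. The Vulnerability section adds limits on age, prisoners, mental handicap and incurable disease, but nothing on allergy. The baseline sheet in Methodology D records study code, age, sex and anatomic site, with no history of reactions.

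**2. Safeguards after the draw**

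Two rules act once the product is on the skin: discretionary withdrawal for severe effects (Methodology B) and immediate stopping for any effect (Risks). Both come after exposure, so neither replaces screening. Their thresholds also differ. They may be meant as separate actions, leaving the study and ending the dressing, but the protocol does not say so.

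**3. Effect on power**

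Inputs from Sample Size and Statistical Analysis: means 8.38 and 7.23, SD 1.5, two-sided 5% level, 80% power.

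- Standardized difference: (8.38 − 7.23)/1.5 = 1.15/1.5 = 0.767.
- Two-sample t-test (noncentral t): 27.70 per group, rounded up to 28. This reproduces the plan's 28 per group, 56 in total. Power at 28 per group is 80.4%.
- If known reactors in one arm lost their day-5 score, with no imputation as the plan states, and the other arm kept 28: 79.7% with one lost, 78.9% with two, 78.0% with three.

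**4. Effect on adverse-effect counts**

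- One reaction in an arm of 28: 1/28 = 3.6 percentage points.
- Two-sided Fisher p for reactions in one arm only, 28 per arm: 0.49 for 2 against 0, 0.24 for 3 against 0, 0.051 for 5 against 0, 0.023 for 6 against 0. One or two extra reactions change the description, not a test result.

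**5. How likely is at least one known reactor in an arm?**

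The documents give no prevalence. As an assumption, let *p* be the proportion of recruits with a known reaction to the dressing used in a given arm. The expected number in 28 is 28*p*, and the chance of at least one is 1 − (1 − *p*)^28.

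| Assumed *p* | Expected in 28 | Chance of at least one |
|---|---|---|
| 1% | 0.3 | 25% |
| 2% | 0.6 | 43% |
| 5% | 1.4 | 76% |
| 10% | 2.8 | 95% |

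These show only that the event is not remote over a plausible range. They do not measure a difference between arms, because *p* for the hydrocolloid and *p* for the film are both unknown.

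**The case against.** The strongest reply is that this is a wording omission with little statistical consequence. Much of that stands, and it rules out three stronger readings that a reader might infer.

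- **That the tolerability comparison is biased against the hydrocolloid.** The documents do not support this. The same criteria apply to everyone before allocation, so antibiotic reactors are absent from both arms and dressing reactors may fall in either. The randomized contrast stays valid for the patients enrolled. Nor is the control arm cleared of reactors to its own product, since film sensitivity is not excluded either. If the film is adhesive, which the protocol does not state, adhesive sensitivity is a gap in both arms. Finally, no tolerability comparison is planned: the specific objectives list six wound parameters, the dummy tables have no adverse-effect rows, and only the general Fisher or chi-square sentence could be stretched to cover one.
- **That a dressing reaction would be counted as infection.** The Scoring Criteria treat a few millimeters of redness, or unclear findings, as no infection. A positive score needs induration or pus. Nothing in the documents suggests that dressing reactions would typically reach that level, or that three trained assessors would misread them.
- **That day-5 losses would fall on the hydrocolloid arm.** Withdrawal is discretionary, and film reactors could equally be lost from the control arm.

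It is also fair to say that irritation is not allergy, that Methodology B's hypersensitivity example refers to either treatment, and that a patient who has been told the risks may decline. The consent form is attached separately and was not available, so a screening question there cannot be ruled out.

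None of this answers the eligibility text itself. It admits known reactors to two of the three products, and an informal question at consent is no substitute for a written criterion.

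**Conclusion.** The gap is real and is mainly one of patient safety. As written, a known reactor to the hydrocolloid or to the control arm's film is eligible and may be assigned it. The omission does not bias the randomized comparison, and the sample size stays at 28 per group. Losing one patient to a reaction costs 0.7 percentage points of power (80.4 − 79.7). The visible effect is on descriptive safety counts, at 3.6 percentage points per reaction.

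Confidence in the textual omission is high. How often it would matter depends on a prevalence that the documents do not give. This is a cheap improvement worth making, not a threat to the trial's conclusions.

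**What to change.** In the Project Summary and in Methodology B, extend the exclusion to known hypersensitivity to any study product in either arm: topical antibiotics, hydrocolloid dressings or their components, and transparent film or adhesive dressings. Check it with one screening question before the draw and record the answer on the baseline sheet, so that every randomized patient is eligible for either allocation.

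The cost is one clause in two places, one question and one data field. The downside is that a few candidates are screened out and must be replaced.

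Separately, reconcile the withdrawal threshold in Methodology B with the stopping threshold under Risks, and state whether they describe one action or two. Which threshold applies is for the investigators to decide.
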